5.2.2.4. Reverse Cumulative Distribution Curves (RCDCs)

Reverse cumulative distribution curves (RCDCs) for RSV A- and RSV B-neutralizing antibody titers for a combination of available time points and vaccine groups will be generated.

5.3. Methods to Manage Missing Data

5.3.1. Safety Data

Standard algorithms on handling missing AE dates and missing AE severity will be applied as described in Pfizer's Vaccine Statistics Rulebook.

5.3.1.1. Reactogenicity Data

For derived variables based on reactogenicity data, if any day of the 7-day e-diary is available, the "any day (Day 1-7)" data will be considered nonmissing.

The reactogenicity data are collected through e-diary, which does not allow participants to skip the question. Therefore, for a specific day, as long as the e-diary data are transferred for that day, all of the reactogenicity data for the participant on that day are nonmissing. No missing reactogenicity data will be imputed other than what is described in [Section 3.5.2](#).

5.3.2. Immunogenicity Data

For GMT and GMC analysis, a titer reported as < lower limit of quantitation (LLOQ) will be converted to a value of $\frac{1}{2}$ LLOQ. For calculating a fold rise, < LLOQ will be converted to $\frac{1}{2}$ LLOQ for a numerator, and < LLOQ will be converted to LLOQ for a denominator when only one of either the numerator or denominator is < LLOQ. If both the numerator and denominator are < LLOQ, then both will be converted in the same way. For any calculations, a titer reported as > upper limit of quantitation (ULOQ) will be converted to a value of ULOQ.

Values that are designated as serum quantity not sufficient (QNS), designated as indeterminate results, or recorded as "Not Done" will be set to missing. No imputation will be done for these missing values.

6. ANALYSES AND SUMMARIES

6.1. Primary Endpoints

6.1.1. Primary Endpoints: Maternal Participants

6.1.1.1. Local Reactions Within 7 Days After Vaccination

- Analysis set: Safety ([Section 4](#)).
- Analysis methodology: Descriptive summary statistics.
- Intercurrent events and missing data: For participants who discontinue, all collected data will be included; intermediate missing values will not be imputed.
- For each group, n, %, and 95% CI will be presented by vaccine group for the following variables:
 - Presence or absence of each local reaction on each day (Days 1-7) after vaccination.

- Presence or absence of each local reaction on “any day (Day 1-7)” after vaccination.
- Presence or absence of any local reaction on “any day (Day 1-7)” after vaccination.
- Maximum severity of each local reaction on “any day (Day 1-7)” after vaccination.
- For each group, n, mean, median, minimum, and maximum will be presented by vaccine group for the following variables:
 - Duration of each local reaction after vaccination.
 - Onset day of each local reaction after vaccination.
 - Onset day of any local reaction after vaccination.

6.1.1.2. Systemic Events Within 7 Days After Vaccination

- Analysis set: Safety ([Section 4](#)).
- Analysis methodology: Descriptive summary statistics.
- Intercurrent events and missing data: For participants who discontinue, all collected data will be included; intermediate missing values will not be imputed.
- For each group, n, %, and 95% CI will be presented by vaccine group for the following variables:
 - Presence or absence of systemic event on each day (Days 1-7) after vaccination.
 - Presence or absence of each systemic event on “any day (Day 1-7)” after vaccination.
 - Presence or absence of any systemic event on “any day (Day 1-7)” after vaccination.
 - Maximum severity of each systemic event on “any day (Day 1-7)” after vaccination.
- For each group, n, mean, median, minimum, and maximum will be presented by vaccine group for the following variables:
 - Duration of each systemic event after vaccination.
 - Onset day of each systemic event after vaccination.
 - Onset day of any systemic event after vaccination.

6.1.1.3. AEs Within 1 Month After Vaccination

- Analysis set: Safety ([Section 4](#)).
- Analysis methodology: Descriptive summary statistics for Tier 3 events; difference and 95% CI between the vaccine group and the placebo group for Tier 2 events.
- Intercurrent events and missing data: For participants who discontinue, all collected data will be included; missing AE dates will be imputed as described in Pfizer's Vaccine Statistics Rulebook.
- For each group, number of participants with AEs within 1 month (30 days) (n), %, and 95% CI will be presented for any AE, each system organ class (SOC), and each PT within each SOC, by vaccine group. For AEs classified as Tier 2 events, difference in proportions and associated 2-sided 95% CI between the vaccine group and the placebo group will be presented.

6.1.1.4. Obstetric Complications, MAEs, and SAEs Throughout the Study

- Analysis set: Safety ([Section 4](#)).
- Analysis methodology: Descriptive summary statistics.
- Intercurrent events and missing data: For participants who discontinue, all collected data will be included; missing AE dates will be imputed as described in Pfizer's Vaccine Statistics Rulebook.
- For each group, number of participants with obstetric complications, MAEs, and SAEs throughout the study (n), %, and 95% CI will be presented for any event, each SOC, and each PT within each SOC, by vaccine group.

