9. STATISTICAL CONSIDERATIONS

Detailed methodology for summary and statistical analyses of the data collected in this study is outlined here and further detailed in a statistical analysis plan (SAP), which will be maintained by the sponsor. The SAP may modify what is outlined in the protocol where appropriate; however, any major modifications of the primary endpoint definitions or their analyses will also be reflected in a protocol amendment.

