9.4.2. Safety Analyses

Endpoint	Statistical Analysis Methods
Primary	
 • The point estimate and exact 2-sided 95% CI will be calculated using the Clopper-Pearson method for the percentage of participants reporting each event for each vaccine group. • A 3-tier approach will be used to summarize AEs. For both Tier 1 and Tier 2 events, the 95% CIs for the difference in percentage of participants reporting the events between the RSV vaccine group and the placebo group will be calculated using the test statistic proposed by Miettinen and Nurminen; in addition, for Tier 1 events, the asymptotic p-values will also be presented for the difference in percentage of participants reporting the events, based on the same test statistic and under the assumption that the test statistic is asymptotically normally distributed. There is no preidentified Tier 1 event for this study. A Medical Dictionary for Regulatory Activities (MedDRA) preferred term is defined as a Tier 2 event if there are 4 or more participants in at least 1 vaccine group reporting the event. 
The safety analyses are based on the safety population. Participants will be summarized by the vaccine group corresponding to the vaccine they (for maternal participants) or their mothers (for infant participants) actually received. Missing e-diary data will not be imputed; missing AE dates and missing AE intensity will be addressed using the Pfizer safety rules.

Secondary	
 • Not applicable (N/A)
CCI	

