10.3.1.1. Definition of MAE

An MAE is defined as a nonserious AE that results in an evaluation at a medical facility.

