In addition, AEs occurring up to 48 hours after blood draws or collection of nasal swabs that are related to study procedures must be reported in the CRF.

A 3-tier approach will be used to summarize AEs. Under this approach, AEs are classified into 1 of 3 tiers. Different analyses will be performed for different tiers (see [Section 6.6.1](#)).

Tier 1 events: These are prespecified events of clinical importance and are maintained in a list in the product's Safety Review Plan.

Tier 2 events: These are events that are not Tier 1 but are "common." A MedDRA preferred term (PT) is defined as a Tier 2 event if there are 4 or more participants in any vaccine group reporting the event within 30 days.

Tier 3 events: These are events that are neither Tier 1 nor Tier 2 events.

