6.1.2. Primary Endpoints: Infant Participants

6.1.2.1. Specific Birth Outcomes

- Analysis set: Safety ([Section 4](#)).
- Analysis methodology: Descriptive summary statistics.
- Intercurrent events and missing data: Analysis will be carried regardless of whether an intercurrent event occurs.
- For each group, number and proportion of participants with each birth outcome will be presented by vaccine group. In addition, difference in proportions and associated 2-sided 95% CI between the vaccine group and the placebo group will be presented.

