6.1.2.2. AEs Within 1 Month of Age

- Analysis set: Safety (Section 4).
- Analysis methodology: Descriptive summary statistics for Tier 3 events; difference and 95% CI between the vaccine group and the placebo group for Tier 2 events.
- Intercurrent events and missing data: For participants who discontinue, all collected data will be included; missing AE dates will be imputed as described in Pfizer's Vaccine Statistics Rulebook.
- For each group, number of participants with AEs **CCI** within 1 month (30 days) (n), %, and 95% CI will be presented for any AE, each SOC, and each PT within each SOC, by vaccine group. For AEs classified as Tier 2 events, difference in proportions and associated 2-sided 95% CI between the vaccine group and the placebo group will be presented.

6.1.2.3. AEs of Special Interest (Major Congenital Anomalies, Developmental Delays), MAEs, and SAEs Through 12 Months of Age

- Analysis set: Safety (Section 4).
- Analysis methodology: Descriptive summary statistics.
- Intercurrent events and missing data: For participants who discontinue, all collected data will be included; missing AE dates will be imputed as described in Pfizer's Vaccine Statistics Rulebook.
- For each group, number of participants with AEs of special interest, MAEs, and SAEs through 12 months of age (n), %, and 95% CI will be presented for any event, each SOC, and each PT within each SOC, by vaccine group. For AEs of special interest, difference in proportions and associated 2-sided 95% CI between the vaccine group and the placebo group will be presented.

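### Whole-study maternal obstetric complications, MAEs and SAEs, and 12-month infant MAEs and SAEs, have no committed placebo difference, and the Tier 2 time window is stated in only one document

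*SAP*

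**What the plan says.** The events in question are primary endpoints (SAP 3.1.1 and 3.1.2).

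- **Maternal, whole study (SAP 6.1.1.4):** "number of participants with obstetric complications, MAEs, and SAEs throughout the study (n), %, and 95% CI will be presented for any event", and likewise by system organ class (SOC) and PT, for each vaccine group. No contrast with placebo is named.
- **Infant, to 12 months (SAP 6.1.2.3):** the same per-group output, then one addition limited to a single event type: "For AEs of special interest, difference in proportions and associated 2-sided 95% CI between the vaccine group and the placebo group will be presented". MAEs and SAEs are not covered by it.

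Elsewhere the SAP writes the contrast down. For 30-day adverse events (6.1.1.3, and 6.1.2.2 for infants): "For AEs classified as Tier 2 events, difference in proportions and associated 2-sided 95% CI between the vaccine group and the placebo group". For birth outcomes (6.1.2.1): "In addition, difference in proportions and associated 2-sided 95% CI between the vaccine group and the placebo group will be presented".

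The two documents define Tier 2 differently. Under protocol 9.4.2 a preferred term is "defined as a Tier 2 event if there are 4 or more participants in at least 1 vaccine group reporting the event". SAP 3.5.1 applies the label "if there are 4 or more participants in any vaccine group reporting the event within 30 days". Protocol 9.4.2 also says that no Tier 1 event has been identified in advance, so Tier 2 is the only tier that yields a difference.

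SAP 5.2.1 provides for a CI of a difference where it is judged suitable, names no endpoint, and fixes the method as Chan-Zhang.

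**The concern.** Safety is the primary objective, the trial has a placebo arm, and this is the vaccine's first study in pregnant women. The natural summary for a primary safety endpoint is the excess over placebo with its uncertainty. For unsolicited events the SAP commits to that summary for the first 30 days, for birth outcomes and for infant events of special interest. It does not commit to it for later maternal complications, MAEs and SAEs, or for later infant MAEs and SAEs.

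A reader who has only per-group intervals will compare them by eye. Two 95% intervals can overlap while the interval for their difference lies wholly above zero, so that comparison can hide an excess. If a difference is added later, someone will have decided with the data in view which rows should get one.

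**Working it through.** The plan gives no figure for this point. Its nearest one, protocol Table 6, reproduces: 1 - 0.99^100 = 0.634 against the stated 63%, and the other 20 cells also agree. The documents give no background event rates, so all event counts and rates below are assumptions.

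**1. How much of follow-up the 30-day window reaches**

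Inputs: vaccination at 24 0/7 (day 168) to 36 0/7 weeks (day 252), from protocol 5.1.1; a 30-day window, from SAP 3.5.1; follow-up to about 12 months after delivery, from protocol 4.1.1. Assumed: vaccination spread evenly over the 84 days, and delivery at 37 0/7 (day 259) to 40 0/7 weeks (day 280).

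A woman delivers after the window closes if she is vaccinated more than 30 days before delivery.

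- Delivery at day 259: vaccinated before day 229, so (229 - 168)/84 = 61/84 = 73%.
- Delivery at day 280: vaccinated before day 250, so (250 - 168)/84 = 82/84 = 98%.

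Maternal follow-up after vaccination runs from (259 - 252) + 365 = 372 days to (280 - 168) + 365 = 477 days. The window covers 30/372 = 8.1% down to 30/477 = 6.3% of it. For infants it covers 30/365 = 8.2%.

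**2. What per-group intervals can hide**

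Assumed 130 per arm (650/5, the planned maximum). Per-group intervals are Clopper-Pearson; the difference uses Chan-Zhang (two one-sided exact tests on the score statistic, 0.025 each side).

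| Vaccine arm | Placebo | Per-group 95% CIs (%) | Difference, points (95% CI) |
|---|---|---|---|
| 12/130 | 4/130 | 4.9 to 15.6; 0.8 to 7.7 (overlap) | +6.2 (0.3 to 12.9) |
| 16/130 | 4/130 | 7.2 to 19.2; 0.8 to 7.7 (overlap) | +9.2 (2.5 to 16.5) |

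Against 4/130, the difference first excludes zero at 12 events and the per-group intervals first separate at 17, so counts of 12 to 16 fall in the gap. The same gap is 9 to 13 against 2/130, 25 to 30 against 13/130, and 10 to 14 against 3/100 with 100 per arm. The Miettinen-Nurminen interval, which protocol 9.4.2 names, gives 0.3 to 12.8 for 12/130 v 4/130, so the illustration does not depend on which document's method is used.

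**3. What the Tier 2 window does to eligibility**

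Take an assumed PT with a true rate of 1% by day 30 and 3% over the study, equal in five groups of 100. With P = Pr(4 or more of 100), the chance that at least one group reaches the threshold is 1 - (1 - P)^5.

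- At 1%: P = 0.018, giving 0.09.
- At 3%: P = 0.353, giving 0.89.

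With 130 per group the two values are 0.19 and 0.98. Whether a later-occurring term gets a difference therefore depends heavily on which definition is used.

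**4. Does the protocol promise more than the SAP delivers?**

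Two readings are fair.

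- *All AEs.* Protocol 10.3.1.1 says "An MAE is defined as a nonserious AE that results in an evaluation at a medical facility", and under 10.3.2 an SAE must first be an AE. Common terms among later MAEs and SAEs then fall under the protocol's unwindowed Tier 2 rule, and the SAP's 30 days removes them.
- *The AE endpoint.* Protocol 3.1 lists 1-month AEs and whole-study complications, MAEs and SAEs as separate primary endpoints. General AE collection stops at about 1 month (8.3.1). The 3-tier wording can refer to the first endpoint only, and then the SAP's 30 days restates an existing window.

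The texts do not settle which is meant.

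**The case against.** The strongest reply is that nothing is broken. The estimands in SAP 2.1.4 are percentages in each vaccine group, protocol 9.4.2.1 promises descriptive evaluation with exact intervals by group, and the SAP delivers that down to PT level. That stands.

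A reader might infer that the SAP has cut an analysis the protocol promised. The documents do not support this: it follows on only one of the two readings above. Protocol 9 also lets the SAP modify the plan; its condition is that "any major modifications of the primary endpoint definitions or their analyses will also be reflected in a protocol amendment", and nothing shows that this change would count as major.

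A reader might also infer that any later comparison would be post hoc throughout. That is too strong. SAP 6.1.1.4 and 6.1.2.3 fix the period and the rows, and 5.2.1 fixes the interval method. Only whether a difference is shown, and for which rows, is left open.

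Third, part of the ground is covered elsewhere. MAEs and SAEs within 30 days can qualify as Tier 2. Birth outcomes, which include vital status and neonatal problems, get a difference, as do congenital anomalies and developmental delay to 12 months. This narrows the gap without closing it for later maternal events or for other later infant MAEs and SAEs.

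Last, the examples in the working were chosen where the interval excludes zero, and SAP 5.1 disclaims decision rules. With equal true rates of 3% to 10% and 130 per arm, about 2% of arm-by-PT comparisons would fall by chance where the per-group intervals overlap but the difference lies above zero. That is a real cost of adding contrasts, and a reason to label them descriptive.

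**Conclusion.** The point holds as a minor, cheap improvement to a descriptive analysis. The visible SAP text makes no commitment to a placebo difference for whole-study maternal obstetric complications, MAEs and SAEs, or for 12-month infant MAEs and SAEs. It does not forbid one. Under the assumed even spread of vaccination and delivery at 37 to 40 weeks, 73% to 98% of women deliver after the 30-day window has closed, so most peripartum maternal events have no committed contrast with placebo. No alpha, power or sample-size figure is affected.

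The Tier 2 window is a matter for reconciliation; a contradiction is not established.

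Reactogenicity is also summarised per group only (SAP 6.1.1.1 and 6.1.1.2), so the comparison made here is among unsolicited events. It should not be inferred that no difference will be reported: SAP 6.6.1 is partly blacked out, although its visible text refers back to 6.1.1 and 6.1.2, and table shells are kept separately. The finding covers the visible text only.

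**What to change.** Add to SAP 6.1.1.4, and to 6.1.2.3 for infant MAEs and SAEs, a sentence such as: *For each vaccine group, the difference from placebo in the percentage of participants affected, with a 2-sided 95% CI by the method of Section 5.2.1, will be shown for any event and for every PT reported by at least 4 participants in any vaccine group over the same period.*

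State one Tier 2 time window in both SAP 3.5.1 and protocol 9.4.2, and say whether the 3-tier approach covers all AEs or only the 1-month AE endpoint.

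A column for any RSV vaccine against placebo is optional. It is a different contrast and can mask an effect confined to one arm, so it belongs only beside the per-arm columns.

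The cost is two sentences and four extra contrasts per row, with no new data. The downside is more unadjusted intervals, some of which will exclude zero by chance. SAP 5.1 and 6.6.1 already provide for reading them as descriptive and unadjusted.

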6.1.2. Primary Endpoints: Infant Participants

6.1.2.1. Specific Birth Outcomes

- Analysis set: Safety ([Section 4](#)).
- Analysis methodology: Descriptive summary statistics.
- Intercurrent events and missing data: Analysis will be carried regardless of whether an intercurrent event occurs.
- For each group, number and proportion of participants with each birth outcome will be presented by vaccine group. In addition, difference in proportions and associated 2-sided 95% CI between the vaccine group and the placebo group will be presented.

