2.1.4.2. Primary Estimands: Infant Participants

- **Percentage of infant participants with specific birth outcomes.**

This estimand includes the following 4 attributes:

- Population: Infant participants born to the maternal participants receiving 1 dose of investigational product.
- Variable: Presence/absence of specific birth outcomes.
- Intercurrent event(s): No intercurrent events to be taken into account.
- Population-level summary: Percentage of infant participants with specific birth outcomes in each vaccine group.

- **Percentage of infant participants having AEs.**

This estimand includes the following 4 attributes:

- Population: Infant participants born to the maternal participants receiving 1 dose of investigational product.
- Variable: Presence/absence of AEs from birth to 1 month, CCI [REDACTED]
- Intercurrent event(s): For participants who discontinue, all collected data will be included; missing AE dates will be imputed as described in Pfizer's Vaccine Statistics Rulebook.
- Population-level summary: Percentage of infant participants with AEs CCI [REDACTED] from birth to 1 month in each vaccine group.

- **Percentage of infant participants having SAEs, AEs of special interest, and MAEs through 12 months of age.**

This estimand includes the following 4 attributes:

- Population: Infant participants born to the maternal participants receiving 1 dose of investigational product.
- Variable: Presence/absence of SAEs, AEs of special interest, and MAEs. These will be collected through 12 months of age, except for those congenital anomalies that occur during intrauterine life and can be identified prenatally, at birth, or later in life.
- Intercurrent event(s): For participants who discontinue, all collected data will be included; missing AE dates will be imputed as described in Pfizer's Vaccine Statistics Rulebook.
- Population-level summary: Percentage of infant participants with the event of interest during the first 12 months of life in each vaccine group.

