3.5.5.2. Physical Examination, Including Vital Signs: Infant Participants

The physical examination will be performed at all scheduled visits and will include any clinically significant abnormalities within the following body systems: general appearance; skin; head, eyes, ears, nose, and throat; heart; lungs; abdomen; back; musculoskeletal; extremities; genitourinary; neurological; and lymph nodes.

Length, head circumference, and weight will also be measured and recorded.

Rectal temperature, heart rate, and respiratory rate will be assessed at all visits; additionally, oxygen saturation by pulse oximetry will be assessed at birth ^{CCI} [REDACTED]. All attempts should be made to help ensure that measurements are taken while the infant is resting quietly.

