3.5.7. Birth Outcome: Infant Participants

Infant outcome at birth will be collected at the delivery visit and includes the following: gestational age (weeks, days); Apgar (appearance, pulse, grimace, activity, and respiration) score at 1, 5, and 10 minutes; Ballard score; infant cry immediately after delivery (yes, no); infant suckle shortly after delivery (yes, no); newborn normal (yes, no); congenital malformation/anomaly (yes, no); and other neonatal problem/abnormality (yes, no). Infant vital status (live, stillbirth) will also be included. Neonatal death will be derived using the

response to “delivery outcome” from the pregnancy outcome and the AE data. Neonatal death is defined as the death of a live-born infant that occurred within a month after birth.

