5.2. General Methods

Descriptive summary statistics will be provided for all endpoints. Unless otherwise explicitly stated, descriptive statistics for continuous variables are n, mean, median, standard deviation, minimum, and maximum. Descriptive statistics for categorical variables are the proportion (%) and the n (the numerator) and N (the denominator) used in the calculation of the proportion.

All analyses for both immunogenicity and safety data will be descriptive in nature.

All of the safety, tolerability, and immunogenicity data will be summarized by vaccine group of the maternal participants. Immunogenicity results will be analyzed separately for all the formulations. Within each participant group (maternal or infant), all participants who receive placebo will be combined as the control group. All data will be presented separately for maternal and infant participants. The only exception is the combined analysis of maternal-to-infant placental transfer ratio (infant/mother) of RSV A– and RSV B-neutralizing antibody titers.

Within maternal and infant groups, immunogenicity results may be summarized by formulation, dose level, and gestational age (GA).

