6.6.4. Physical Examination, Including Vital Signs

Descriptive summaries (counts and percentages) and listings based on the safety population will be provided in accordance with the Pfizer reporting standards. All summaries and listings for these data will be generated separately for maternal and infant participants.

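### The only vaccine-placebo contrast planned for infant birth outcomes is a difference in proportions, so a moderate shift in gestational age at birth is poorly detected by it

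*SAP*

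**What the plan says.** The infant estimand in SAP 2.1.4.2 is binary: "Variable: Presence/absence of specific birth outcomes". SAP 6.1.2.1 names descriptive summary statistics as the method, says that the "number and proportion of participants with each birth outcome will be presented by vaccine group", and then specifies the comparison: "In addition, difference in proportions and associated 2-sided 95% CI between the vaccine group and the placebo group will be presented".

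SAP 3.5.7 lists what is collected as infant outcome at birth. Some items are measured: "gestational age (weeks, days); Apgar (appearance, pulse, grimace, activity, and respiration) score at 1, 5, and 10 minutes; Ballard score". Others are yes/no, for example "newborn normal (yes, no); congenital malformation/anomaly (yes, no); and other neonatal problem/abnormality (yes, no"). The visible text gives no cut-point that would turn gestational age, Apgar or Ballard score into a proportion.

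SAP 5.2 promises descriptive statistics for all endpoints and sets a default: "Unless otherwise explicitly stated, descriptive statistics for continuous variables are n, mean, median, standard deviation, minimum, and maximum". SAP 5.2.2 adds a Student's t interval for a mean. SAP 5.2.2.3 applies the two-sample t method to differences between groups, but only for log-transformed antibody levels.

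Birth weight is not in the SAP 3.5.7 list. It falls under the infant physical examination (SAP 3.5.5.2), for which SAP 6.6.4 mentions counts and percentages and refers to sponsor reporting standards.

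**The concern.** For this endpoint the SAP goes beyond group summaries and asks for a placebo contrast with an interval, but only in a form that suits the yes/no items. To follow it for gestational age, the weeks-and-days value has to be cut into categories, which discards how early or late each birth was.

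This is the first study of the vaccine in pregnant women (Protocol 2.1), infant safety is a primary objective, and SAP 2 says the results will inform whether to proceed to efficacy studies. SAP 5.1 relies on estimation rather than testing, so the width and sensitivity of the reported intervals are what count. If vaccination shortened gestation by a moderate amount across the group, the planned interval for a proportion would often include zero when an interval for the mean, from the same data, would not.

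**Working it through.** **The plan's own figure.** The only sample-size figure is Protocol Table 6, the probability of seeing at least one event, 1 − (1 − p)^n. For p = 1% and n = 100 this is 1 − 0.99^100 = 0.634, against 0.63 stated. All 21 cells reproduce. The table does not address shifts in a measured scale.

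**Inputs from the documents.** There are 100 women per vaccine dose/formulation on the northern-hemisphere basis (Protocol 9.2) and at most 650/5 = 130 per group. Infant numbers are taken as equal to maternal numbers. Intervals are two-sided 95%.

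**Inputs assumed.** Gestational age at birth is roughly normal with mean 39.2 weeks on placebo and SD 1.6 (range 1.3 to 1.9). The illustrative cut is below 37 weeks. The vaccine group's mean is 0.5 weeks shorter (range 0.3 to 0.7).

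**Mean difference.** SE = SD × √(2/n), noncentrality = shift/SE, power from the noncentral t.
- n = 100: SE = 1.6 × √0.02 = 0.226; 0.5/0.226 = 2.21; chance that the CI excludes zero 59%. CI half-width 1.972 × 0.226 = 0.45 weeks.
- n = 130: SE = 0.198; 0.5/0.198 = 2.52; chance 71%. Half-width 0.39 weeks.

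**Proportion difference.** Placebo rate Φ((37 − 39.2)/1.6) = Φ(−1.375) = 8.5%. Vaccine rate Φ((37 − 38.7)/1.6) = Φ(−1.0625) = 14.4%. Difference 5.94 points. Power ≈ Φ((0.0594 − 1.96 × SE0)/SE1), where SE0 uses the pooled rate and SE1 the separate rates.
- n = 100: SE0 = 0.0450, SE1 = 0.0448; Φ(−0.64) = 26%.
- n = 130: SE0 = 0.0395, SE1 = 0.0393; Φ(−0.46) = 32%.

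**Pooled vaccine against placebo, 520 v 130.** The same formulas with unequal groups give 89% against 42%.

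**Range.** The gain from the mean difference over SD 1.3 to 1.9, shifts of 0.3 to 0.7 weeks and 100 to 130 per arm is 9 to 52 percentage points. At 0.5 weeks the mean difference succeeds in 46 to 87% of cases. At 0.3 weeks it succeeds in only 20 to 46%, so it usually misses, and the proportion does worse still.

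**Check free of weeks.** For a shift of 0.4 SD at 100 per arm, the mean difference gives 81%. A cut that 3%, 5% or 10% of placebo infants fall beyond gives 25%, 32% or 43%. A cut at the placebo median gives 61%. Replacing the z approximation by Fisher's exact test, a rough stand-in for the exact Chan-Zhang interval in SAP 5.2.1, lowers the 3 to 10% figures to 15 to 37%.

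**Where the ranking reverses.** A simulation (3,000 runs) put 4% of placebo births and 12% of vaccine births near 35 weeks and left the rest unchanged. It gave 34% for the mean difference and 47% for the proportion. The exact values depend on the assumed spread and arm size. The ordering held on repetition with SDs of 1.1 to 1.6 weeks for the remaining births and 100 or 130 per arm.

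**The case against.** The study is descriptive, with no hypothesis, decision rule or power target, so the chance of excluding zero is a borrowed yardstick and no documented figure is wrong. That stands. Here it serves only to compare how sensitive two intervals from the same data are.

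A reader might infer that shifts in gestational age would be largely undetectable in this trial. The documents do not support that. The SAP 5.2 default plausibly gives n, mean, median, SD and range by vaccine group, from which a mean difference and its interval can be computed by hand. SAP 3.5.6 also collects premature live birth as a delivery outcome, and SAP 6.6.5 summarises pregnancy outcomes. What is missing is a specified contrast, not the information. One doubt remains: the default yields where something else is explicitly stated, and SAP 6.1.2.1 explicitly states proportions. This is an ambiguity in wording, and the mock-up tables that might settle it are kept separately.

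A reader might also infer that the full scale would usually reveal shifts that the proportion misses. That fails at 0.3 weeks and for harm confined to the tail.

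It can fairly be said that SAP 3.5.7 only lists collected items, so the scales need not all be analysed as proportions. Even on that reading, no section plans a placebo contrast for them in any other form.

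Lastly, a wide programme of added contrasts would have a real cost. Weight, length and head circumference at 6 visits in 4 vaccine arms would make 3 × 6 × 4 = 72 unadjusted intervals, mostly outside this endpoint. That objection is accepted and the fix is kept narrow.

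**Conclusion.** The point holds in a limited form. For a primary infant endpoint that includes gestational age in weeks and days, the plan specifies a placebo contrast only on the proportion scale. A moderate, group-wide shift is poorly detected by that contrast: about 26 to 32% for 0.5 weeks, against 59 to 71% for a mean difference, at 100 to 130 per arm.

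These sizes rest on an assumed mean, SD, normal shape and 37-week cut, none of which is in the documents. A more central cut would narrow the gap. Neither scale is better for every kind of harm, so the mean difference belongs beside the proportions and should not replace them. Rank-based Apgar contrasts and growth contrasts at every visit are matters of preference and not part of this conclusion.

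**What to change.** In SAP 6.1.2.1:
- Keep the proportions and their differences as planned.
- State that the SAP 5.2 continuous summaries apply to gestational age at birth, Apgar and Ballard score.
- Add the vaccine-minus-placebo mean difference in gestational age at birth, with a two-sided 95% CI by the two-sample t method, for each vaccine group and for pooled vaccine against placebo. Label it descriptive, so that the percentage estimand in SAP 2.1.4.2 stays as it is.
- Optionally, do the same for Ballard score and birth weight.

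The cost is a few lines of text and some table columns, with no new data. Gestational age alone adds 4 + 1 = 5 unadjusted intervals, and all three variables add 15. With no true differences, about 15 × 0.05 = 0.75 of those would be expected to exclude zero by chance, so the table should carry a note saying that the intervals are not adjusted for multiplicity.
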